17. STATISTICAL ANALYSES

Interpretation of scores and score differences in patient-reported measures can be a difficult task since the scales lack the clinical meaning that is inherent in measures of survival, serum concentrations, or anthropometric values. To aid in interpretation of these scores, differences are often standardized by dividing by the standard deviation in the sample to calculate an effect size. There are general guidelines for small, moderate, and large effects on this standardized scale that can be applied to any outcome measure. A standardized effect size (mean difference / standard deviation) less than 0.20 is considered clinically insignificant in the field of patient-reported outcomes research, while effect sizes of 0.30 - 0.40 are generally considered to be minimally important to moderate in magnitude.

For the CIRS, which had a standard deviation of 3.6 in a sample of patients receiving cyclosporine, an effect size of 0.30 corresponds to a difference of 1 point on the 0-20 scale. In the control group, we expect a mean CIRS score similar to or higher than that seen in a sample of patients receiving cyclosporine (3.8 +/- 3.6). A 1 point reduction in the Envarsus XR® group would be equivalent to a 30% reduction in calcineurin inhibitor-related symptoms.

A total of 240 patients will be enrolled. Estimating 15% study dropout provides 204 patients with complete data at the study endpoint, which will allow us to detect effect sizes of 0.28 or larger for the difference between treatment arms with a 2-sided 0.05 level of significance and 80% power in for individual patient reported outcome measure items. This sample size is also appropriately powered to compare adherence rates between groups. Based on assumptions of 75% and 90% mean adherence, respectively, in the 2 groups (and standard deviations of 38% and 30%, respectively), a sample size of 110 per group will yield 90% power to obtain a significant difference between the 2 groups, using a 2-sample t test at a 2-sided 0.05 level of significance.

For analyses of the CIRS, TRS, and PROMIS-29 scores, we will first calculate change within individuals from enrollment to 12 months. Analysis of covariance (ANCOVA) will be used to compare change between treatments, adjusted for baseline score. The ANCOVA model-estimated mean difference between treatments will be divided by the pooled baseline standard deviation to calculate effect size measures to aid in interpretation. Medication adherence and change in eGFR will be compared between groups using similar models.

For analyses of individual transplant-related symptoms and side effect bother (GP5), within-patient change on each item will be classified as improved, worsened or unchanged and compared between treatments using chi-square tests for ordinal data. Medication satisfaction responses at 12 months will be compared between treatments using an ordinal chi-square test.

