3. OBJECTIVE AND ENDPOINTS

Primary Objective: The primary objective of the study is to determine if treatment with Envarsus XR® reduces a group of side effects that are commonly associated with calcineurin-inhibitor therapy.

Overall Hypothesis: Treatment with Envarsus XR® leads to improved total *calcineurin inhibitor-related symptom (CIRS) score* at 1 year after kidney transplantation compared to immediate-release, twice-daily tacrolimus.

Clinical Study Protocol [#SIMPLE]

Primary Endpoint: Difference in mean calcineurin inhibitor-related symptoms severity score at 12 months post- kidney transplantation in Envarsus XR® group vs Control (immediate-release, twice-daily tacrolimus) group.

The CIRS is a questionnaire that assesses five symptoms (from PRO-CTCAE) that have been shown to be associated with calcineurin inhibitors. These symptoms include trembling hands, muscle cramps, muscle weakness, swollen gums, and increased hair growth. Each symptom is based on symptom severity in the last 7 days scaled from 0 (none) – 4 (very severe). The cumulative score ranges from 0-20. Based on internal data, we expect a mean CIRS score in the control group (immediate release tacrolimus) to be around 3.8 ± 3.6 and hypothesize a 30% reduction in the Envarsus XR® group. This reduction is equivalent to a 1 point difference on the 0-20 scale or a standardized effect size (mean difference / standard deviation) of 0.29.

Secondary Endpoints:

1. Reduction in the population mean of any one of the five individual CIRS item including: trembling hands, muscle cramps, muscle weakness, swollen gums, and increased hair growth between the two treatment groups at 12 months
2. Total percent of patients in each treatment group with a severe or very severe score (3 or 4) on any CIRS item 12 months.
3. Difference in mean transplant-related symptoms (TRS) score between treatments at 12 months post-transplant.

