8. TREATMENT ASSIGNMENT

This is an observational study, and as such, treatment will not be assigned, and there is no intervention. The treatment decision will be made by each patient's transplant care team, independent of the study.

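### Section 17's claim of 80% power for 0.28 SD with 204 completers does not follow from its stated inputs: two equal groups have 51% power unadjusted, and the planned ANCOVA gets there only at an unstated correlation near 0.70

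*Combined protocol and SAP*

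**What the plan says.** Section 17 (Statistical Analyses) opens its sample-size paragraph with "A total of 240 patients will be enrolled". After 15% dropout, it says, this "provides 204 patients with complete data at the study endpoint, which will allow us to detect effect sizes of 0.28 or larger". The effect in question is the contrast of the two arms, and the claim is made at a two-sided 0.05 level with "80% power in for individual patient reported outcome measure items".

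For the CIRS, TRS and PROMIS-29 scores, the same section says: "Analysis of covariance (ANCOVA) will be used to compare change between treatments, adjusted for baseline score". The resulting difference is then divided by the pooled baseline SD to give an effect size. Individual transplant-related symptoms and GP5 are handled differently: "within-patient change on each item will be classified as improved, worsened or unchanged and compared between treatments using chi-square tests for ordinal data".

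Section 8 (Treatment Assignment) states that "treatment will not be assigned, and there is no intervention". No expected mix of the two formulations is given.

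The target effect on the primary endpoint appears in several forms. The Synopsis and Section 3 take a control mean of 3.8 (SD 3.6) and hypothesise a 30% reduction. Section 3 adds "This reduction is equivalent to a 1 point difference on the 0-20 scale", or 0.29 SD. Section 17 equates 1 point with 0.30 SD and says "A 1 point reduction in the Envarsus XR® group would be equivalent to a 30% reduction in calcineurin inhibitor-related symptoms".

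**The concern.** 204 is the total number of completers, so a two-group comparison has at most 102 per group. A detectable effect of 0.28 SD is small for groups of that size. Baseline adjustment can shrink it, but by an amount that depends on a correlation the documents never give. The gain is also unavailable to the individual items that the sentence names.

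The claimed detectable effect coincides with the effect hypothesised for the primary endpoint (1 point, about 0.28 to 0.30 SD). The natural reading is therefore that the study finds its target effect four times in five. If true power is well below that, a null result will be given too much weight as evidence against the hypothesis, most of all for individual items.

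**Working it through.** **Inputs from Section 17.** 240 enrolled; 15% dropout; two-sided alpha 0.05; power 80%; claimed detectable effect 0.28 SD; CIRS SD 3.6; control mean 3.8. **Assumed, because not stated:** equal groups, the correlation *r* between baseline and 12-month scores, and the ratio *k* of 12-month SD to baseline SD.

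**1. Completers.** 240 × 0.85 = 204, as stated; 102 per group if equal.

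**2. Check on method.** The adherence figure in the same paragraph names a two-sample t test. Pooled SD = √((38² + 30²)/2) = 34.2, so the effect is 15/34.2 = 0.438. With 110 per group, power is 90% by the normal approximation and 89.9% by noncentral t, matching the plan. (At 102 per group it is about 88%.)

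**3. The 0.28 claim, unadjusted, 102 vs 102.** The standard error in SD units is √(2/102) = 0.140.
- Noncentrality at 0.28: 0.28/0.140 = 2.00. Power ≈ Φ(2.00 − 1.96) = 51.6%; noncentral t gives 51.2%. At 0.29 it is 54% and at 0.30 it is 57%.
- Detectable at 80%: (1.960 + 0.842) × 0.140 = 0.392; noncentral t gives 0.394. Then 0.394 × 3.6 = 1.42 CIRS points.
- 80% power at 0.28 would need about 201 to 202 completers per group.

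**4. Under the planned ANCOVA.** The detectable effect in baseline SDs is 0.394 × *k* × √(1 − *r*²). With *k* = 1:

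| Assumed *r* | Detectable at 80% | Power at 0.28 | Power at 0.30 |
|---|---|---|---|
| 0.3 | 0.376 | 55% | 61% |
| 0.5 | 0.341 | 63% | 69% |
| 0.6 | 0.315 | 70% | 76% |
| 0.7 | 0.282 | 80% (79.6%) | 85% |

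Solving 0.394 × √(1 − *r*²) = 0.28 gives *r* = 0.704. With *k* = 0.85 the required *r* is 0.55; with *k* = 1.15 it is 0.79.

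**5. Unequal groups (illustrative splits of 204).** 68 vs 136: detectable 0.418 unadjusted, required *r* 0.74. 51 vs 153: detectable 0.455, required *r* 0.79.

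**6. Items tested in three ordered categories.** I simulated an ordinal trend test, 102 vs 102, with a normal latent change cut into improved/unchanged/worsened at five assumed control splits. A shift of 0.28 SD of item change gives 39% to 43% power. If the shift is instead 0.28 baseline SDs, it equals 0.28/√(2(1 − *r*)) SDs of change: about 30% to 33% power at *r* = 0.3 and 59% to 63% at *r* = 0.7.

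**7. Where 0.28 could come from.** It matches 204 *per group* (detectable 0.278, power 80.5% at 0.28) or a one-sample test on 102 patients (detectable 0.280). Neither is the stated design, and the documents do not show which basis, if any, was used.

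**8. Target effect.** 1/3.6 = 0.28 SD and 1/3.8 = 26%. A 30% reduction is 0.30 × 3.8 = 1.14 points, and 1.14/3.6 = 0.32 SD. The four stated versions (30%, 1 point, 0.29, 0.30) do not line up.

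**9. Precision of the primary comparison.** The 95% half-width is 1.972 × 3.6 × √(1 − *r*²) × √(2/102): ±0.99 points at *r* = 0, ±0.86 at 0.5 and ±0.71 at 0.7.

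**The case against.** The best defence is that the analysis is ANCOVA, under which 0.28 is attainable: at *r* = 0.7 the power is practically 80%, and if scores vary less at 12 months than at baseline a lower correlation is enough. The sponsor may have had such a value in mind. This stands to the extent that the claim cannot be called impossible. It does not supply the missing assumption: baseline lies within 30 days of transplant and the endpoint is about a year later, so a correlation near 0.70 has to be stated and supported.

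Power also looks better at the larger readings of the target: ANCOVA reaches 80% at *r* ≈ 0.65 for 0.30 SD and at *r* ≈ 0.6 for 0.32 SD. That is correct, but the sentence claims 0.28.

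The sentence speaks of individual items, not the CIRS total, so applying it to the primary endpoint is a reading. It is the natural one, since no other power statement covers the CIRS. The ordinal test is specified only for transplant-related symptoms and GP5; individual CIRS items are compared by means in Section 3, and Section 17 names no test for them. The item-level power figures depend on the scale chosen for the shift, but every version falls well short of 80%.

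Finally, this is a pilot study, and version 3.0 (April 2021) is dated about a month before the estimated last completion, so the correction will not change recruitment. It does change how the results should be read.

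**Conclusion.** The concern holds. On the stated inputs, the 80% power claim for 0.28 SD is not reproduced. Power is 51% unadjusted, with a detectable effect of 0.39 SD. Under ANCOVA it is 55% to 70% for assumed correlations of 0.3 to 0.6, and reaches 80% only near 0.70. These figures assume equal groups, which is the best case for 204 patients in a study that does not assign treatment; the ANCOVA figures also assume equal SDs at the two visits and no baseline imbalance. For the items analysed as improved, worsened or unchanged, the claim has no supporting calculation, and power is roughly 30% to 63% across the scenarios tried. The inconsistent target effect is a smaller, related fault. This should be fixed, but it does not invalidate the planned analysis.

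**What to change.** Replace the sentence in Section 17 with wording such as: '204 completers (102 per group if equal) give 80% power at two-sided 0.05 for 0.39 SD unadjusted, about 1.4 CIRS points at SD 3.6. Under baseline-adjusted ANCOVA the detectable effect is 0.38, 0.34 or 0.32 SD if the baseline-to-12-month correlation is 0.3, 0.5 or 0.6, and 0.28 SD only if it is about 0.70 (assumed values; equal SDs).' If the sponsor has data supporting a particular correlation, give that value and its source instead.

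In addition:
- Add one line for unequal groups, using the expected formulation mix.
- Remove the 0.28 claim for individual items. If a claim for individual CIRS items is wanted, name the test and its assumptions.
- Use one target effect in the Synopsis, Section 3 and Section 17: either 1 point (26%, 0.28 SD) or 30% (1.14 points, 0.32 SD).
- Report the primary difference with its 95% confidence interval.

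The cost is wording only: no extra patients and no change to recruitment, data collection or analysis. The stated sensitivity becomes less favourable.

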7. STUDY DESIGN

Study Center(s): Multicenter Transplant Alliance – Kidney Centers

Study Design: This is a prospective, multi-center, observational, open-label, study comparing transplant-specific patient reported outcomes and medication adherence between Envarsus XR® and immediate release tacrolimus medication in adult renal transplant recipients. The study will enroll 240 patients and survey these same 240 patients at three time points during the study.

Clinical Study Protocol [#SIMPLE]

Study Design Rationale:

Patients will be enrolled into the study within the first 30 days post-transplant. Treatment will not be determined by this study, and there is no intervention. The treatment decision will be made by each patient's transplant care team, independent of the study.

For the primary objective, comparison of calcineurin inhibitor related symptoms, a standard two-group design will be used to compare treatment groups. These groups will also be compared for transplant-related symptoms, health-related quality of life, adverse events, patient satisfaction, adherence, dnDSA, and graft function.

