9. STUDY METHODS AND PROCEDURES

General: Transplant recipients will be cared for according to the site's standard of care (SOC) protocols employed for post-transplant follow-up. The investigator at the site will be directly responsible for supervising the care of these recipients during the length of the study.

Products Studied:

- Tacrolimus (twice daily immediate release (IR) oral formulation) or
- Envarsus XR® (a once daily extended-release oral tacrolimus formulation).

Envarsus XR® is an FDA approved medication and is indicated for the prevention of organ rejection in de novo kidney transplant patients in combination with other immunosuppressants

Medication Safety and Efficacy: Renal function, occurrence of biopsy proven acute rejection, development of dnDSA, and occurrence of adverse events will be assessed throughout the duration of the study as collected as part of standard of care or as part of study. Please see Criteria for Evaluation (Section 17) for detailed description of monitoring techniques.

Patient-Reported Measures:

- Patients will complete surveys on their own unless they are unable to. Surveys will be administered on tablets so that data will be recorded in the study's database immediately and securely. The following patient reported outcome measures will be assessed at both study visits.
 - HRQoL: PROMIS -29 profile (29 questions) measuring depression, anxiety, fatigue, pain interference, sleep disturbance, physical function, participation in social roles, and pain intensity
 - Symptoms: Calcineurin-inhibitor related symptoms (5 items) and the Transplant related symptoms (15 items) – items from PRO-CTCAE or in PRO-CTCAE format.
 - Symptoms/Tolerability: FACT- G (GP5) – Single item bothersome assessment (1 question).
 - The PROMIS Self-Efficacy for Managing Medication and Treatment (26 questions).

Clinical Study Protocol [#SIMPLE]

- The Transplant Satisfaction Questionnaire for Medication – question 14.

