10. DEVIATION FROM TREATMENT REGIMEN

If deviation occurs from treatment, patient will continue study. Patient reported outcome measures will be completed as scheduled and samples will be taken as scheduled. Reason(s) for deviation will be recorded.

Criteria for Study Termination

The investigator can discontinue the study participant at any time for any reason, including development of severe adverse events, uncontrolled infection, or other clinical/administrative reasons. Allograft loss and death will be cause for automatic withdrawal from the study. If a patient unable to continue the study for any reason, an early termination visit is necessary to complete the study. If the patient needs to be started on immunosuppression that is listed in the exclusion criteria of this study, an early termination visit is necessary to complete the study.

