12. CONCOMITANT MEDICATIONS

Subjects are required to take immunosuppressive medication to maintain allograft function. The patients will be on the following immunosuppression medications in addition to tacrolimus at the time of study entry per the inclusion criteria:

- *Mycophenolate Mofetil (CellCept®) or Mycophenolate Sodium, Enteric Coated (Myfortic®) (MMF) or generic equivalent formulations.* Target MMF doses will be between 1000 – 3000 mg/day in divided doses or the enteric coated equivalent delivered by mouth twice daily. The MMF dosage will be decreased or discontinued in the presence of adverse events as clinically warranted. Dose reduction or discontinuation will be documented. Adverse events that may warrant dosage modifications of MMF include but are not limited to gastrointestinal (gastritis, diarrhea, nausea, vomiting, dyspepsia) or hematological (leukopenia, thrombocytopenia, anemia or neutropenia). MMF may be resumed at the full dose or at a reduced dose after resolution of symptoms or the patient may receive an alternate adjunctive immunosuppression per the investigator's discretion as long as they are not those listed in the exclusion criteria.
- *Corticosteroids.* Low dose once daily oral prednisone (5-10 mg) may be administered per each site's standard of practice. Doses may be increased at the discretion of the investigator. This most commonly occurs after pulse steroid treatment for rejection.
- *Belatacept, mTOR inhibitors, azathioprine, and investigational immunosuppression* will not be allowed in this study. Patient who are deemed to require one of these medications should be removed from the study and undergo an early termination visit to complete the study.

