15. DATA COLLECTION

Data will be collected at each of the MTAK sites and entered into REDCap. REDCap is a secure web application for building and managing online surveys and databases. REDcap is secure and will be managed by Mayo Clinic Rochester. REDcap is 21 CFR Part 11, FISMA, and HIPPA compliant and hosted on Mayo Clinic's secure servers.

Demographic information: Sex, race/ethnicity, transplant characteristics, and age will be collected.

Medical History: Data to be collected will include medical history and medications, pathologic and laboratory data that are in the pre and post-transplant record.

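### Care teams choose the formulation, but the primary ANCOVA adjusts only for baseline CIRS, leaving the estimate at risk of confounding by centre and recorded patient factors

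*Combined protocol and SAP*

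**What the plan says.** Section 8 of the protocol describes an observational study: "The treatment decision will be made by each patient's transplant care team, independent of the study". Sections 9 and 12 tie management to the centre. Section 9 states: "Transplant recipients will be cared for according to the site's standard of care (SOC) protocols employed for post-transplant follow-up". Section 12 says of low-dose prednisone that it "may be administered per each site's standard of practice". Section 7 nevertheless says that "a standard two-group design will be used to compare treatment groups" for the primary objective.

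Section 17 gives the primary model. Change in CIRS from enrolment to 12 months is calculated for each patient, and "Analysis of covariance (ANCOVA) will be used to compare change between treatments, adjusted for baseline score". TRS and PROMIS-29 use the same model, and adherence and eGFR change use similar ones. Neither the synopsis nor the protocol body adds centre, another covariate, a propensity score, matching, weighting or a sensitivity analysis for non-random choice.

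Usable data are collected. Section 15 states: "Sex, race/ethnicity, transplant characteristics, and age will be collected", and also: "Data to be collected will include medical history and medications, pathologic and laboratory data that are in the pre and post-transplant record". Section 4 admits both living and deceased donor recipients. On departures from treatment, Section 10 says: "Reason(s) for deviation will be recorded". No section records why a formulation was chosen at the start.

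**The concern.** Section 3 asks whether Envarsus XR reduces calcineurin-inhibitor side effects and hypothesises that it leads to a better CIRS score. The synopsis words the objective more softly, as patients on Envarsus XR reporting fewer side effects. Under either wording, a comparison adjusted only for baseline CIRS can mix the formulation with who received it and where.

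Nothing in the design prevents centres or patient types from differing between the groups, and the plan has no step that would show it if they do. An apparent benefit, or the lack of one, could then come partly from selection. Baseline CIRS removes some of this, but not centre practice that acts on symptoms after Visit 1, nor the part of a patient factor's effect on month-12 symptoms that the baseline score does not carry.

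**Working it through.** **The plan's own figures.** Section 17 gives 240 × 0.85 = 204 completers, SD 3.6, a 1-point target, two-sided alpha 0.05, 80% power and a detectable effect of 0.28. Split equally, 204 is 102 per group; the equal split is assumed, since no ratio is stated for CIRS. The unadjusted detectable effect is (1.960 + 0.842) × √(2/102) = 0.392 SD, or 1.41 points. The stated 0.28 appears with 204 per group (0.277), or under ANCOVA if the baseline to month-12 correlation is about 0.70, which the documents do not give. That mismatch is a separate matter, and the point here does not depend on it.

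**Bias from one omitted factor.** Assume a correlation of 0.5 between baseline and month-12 CIRS, equal SDs and no drug effect. Let d be the between-group imbalance in the factor (in SD), and c12 and c0 its correlations with month-12 and baseline CIRS. The imbalance shifts the month-12 score by 3.6 × d × c12 and the baseline score by 3.6 × d × c0. ANCOVA removes 0.5 of the baseline shift, so

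bias = 3.6 × d × (c12 − 0.5 × c0).

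The standard error is 3.6 × √(0.75 × 2/102) = 0.437 points. False-positive rates are simulated. As a hand check, 0.54/0.437 = 1.24, and P(Z > 1.96 − 1.24) is about 24%.

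| d | c12 | c0 | Bias (points) | False positives |
|---|---|---|---|---|
| 0.5 | 0.3 | 0.3 | 0.27 | 9% |
| 0.5 | 0.3 | 0 | 0.54 | 24% |
| 0.5 | 0.2 | 0.4 | 0.00 | 5% |
| 0.75 | 0.4 | 0.4 | 0.54 | 23% |
| 0.75 | 0.4 | 0.2 | 0.81 | 45% |
| 0.75 | 0.4 | 0.1 | 0.945 | 58% |
| 0.75 | 0.4 | 0 | 1.08 | 69% |

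The bias can go in either direction. It is zero whenever c0 = 2 × c12. These rows are chosen scenarios and do not bound the bias. Adjusting for a proxy that captures half of the factor's variance takes the second row from 0.54 to 0.27 points and from 24% to 10%.

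**Precision after adjustment.** SE = 3.6 × √[(1 − 0.5²)(2/102)/(1 − R²)], where R² is the share of formulation choice explained by the added covariates. The adjusted rows use 14 covariate degrees of freedom: baseline 1, centre 5, age 1, sex 1, race/ethnicity 3 (assumed), donor type 1 and medical history 2 (assumed). Detectable difference and power come from the noncentral t distribution.

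| Model | R² | SE | Detectable at 80% power | Power for 1 point |
|---|---|---|---|---|
| Baseline only | 0 | 0.437 | 1.23 | 63% |
| Adjusted | 0.10 | 0.460 | 1.30 | 58% |
| Adjusted | 0.30 | 0.522 | 1.47 | 48% |
| Adjusted | 0.50 | 0.617 | 1.74 | 36% |

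If the covariates also cut residual variance by 10%, the adjusted rows become 1.23, 1.39 and 1.65 points, with power of 63%, 52% and 40%.

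**The case against.** The strongest reply is that the study is openly an observational pilot, discloses that treatment is not assigned, already adjusts for baseline CIRS, and would lose power from further adjustment. Part of this stands. Baseline adjustment is real protection: when a factor is equally related to both scores it halves the bias, and it can remove it altogether. The 24% figure needs a factor wholly unrelated to baseline CIRS, which is the less favourable assumption. The precision loss is real too. Centre adjustment can also do harm: if centre drives formulation choice but hardly affects CIRS, it costs precision and can amplify bias from unmeasured factors.

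The pilot label does not remove the point, because Section 3 states a directional hypothesis and Section 17 sets a formal alpha and power. Nor does the first title line, which calls the study randomized: the version 3.0 protocol title and Sections 7 and 8 describe an observational study.

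A reader might infer that the primary estimate is in fact confounded, or that it cannot separate formulation from patient mix at all. The documents do not support that. They report no formulation use by centre or patient type, and baseline adjustment removes part of any difference. Nor should the illustrative figures be read as a forecast of the false-positive rate.

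**Conclusion.** The point holds as a risk of bias in the stated primary analysis. The model in Section 17 is specific, omits centre and every recorded patient factor except baseline score, and cannot on its own support the causal wording of Section 3. The size and direction of any bias are unknown.

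On the assumed inputs, a moderate omitted factor produces roughly a quarter to a half of the 1-point target (0.27 to 0.54 points). A stronger one (0.75 SD imbalance, c12 of 0.4) produces 0.54 to 1.08 points as c0 falls from 0.4 to 0. The imbalances, the correlations, the equal split and normal scores are all assumptions. Six enrolling centres is a further one: the protocol's list has six institutions, one of them a research institute, and no section says that all six enrol. Only the precision figures depend on it.

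This is a cheap improvement. Adjustment deals only with recorded factors, so the result remains an association.

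**What to change.** In Section 17, make the primary analysis an ANCOVA of CIRS change on treatment, baseline CIRS, enrolling centre and a short list of pre-treatment factors from Section 15. Examples are age, sex, race/ethnicity, donor type, relevant medical history and, if recorded before or at the start of tacrolimus, planned steroid use. Fix and date the list before any outcome is compared by formulation; version 3.0 is dated 08APR2021, and last completion was estimated for May 2021. Use the same covariates for TRS, PROMIS-29, adherence and eGFR, with each outcome's own baseline where one exists.

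Tabulate formulation by centre, and report the model with and without centre. If every centre uses a single formulation, the centre-adjusted contrast cannot be estimated; say so and make no formulation claim. Keep the baseline-only ANCOVA as a sensitivity analysis. Overlap weighting and an E-value are optional.

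Visit 1 may fall anywhere in the first 30 days, so baseline may already reflect treatment. If a check on this is wanted, model the 12-month score with the covariates but without baseline CIRS. Dropping baseline from a change-score model makes matters worse, because change still subtracts it in full. With an assumed true effect of −1.0 at month 12, −0.5 already present at Visit 1, and no confounding, the stated ANCOVA gives −1.0 + 0.5 × 0.5 = −0.75, change without the covariate gives about −0.5, and the 12-month score gives −1.0.

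Restate the detectable difference and word the conclusion as an adjusted association. The cost is analysis wording, one table and modest programming on data already planned (assuming donor type is recorded under transplant characteristics), plus the loss of precision shown in the working.
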